Title of Project

Effect of Pulsatile Pressure and Long Sleep Duration on Cerebral Vascular Function

Agency and Award Number

American Heart Association, Award Number 19IPLOI34760579

Date

Last Updated Study Protocol and Statistical Analysis Plan: April 12, 2022

Document Type

Study Protocol and Statistical Analysis Plan

Comment

Study protocol described below can also be read in the Methods sections within two published articles.

Study Design

Relevant to Primary Outcomes

This study utilized a randomized, crossover design that consisted of five consecutive nights of 8 or 11 hours time in bed (TIB) each night that participants completed at home. Participants were randomly assigned based on a random allocation sequence generated in Microsoft Excel. The 8 hours TIB protocol served as a control sleep condition with the intent that participants would achieve the recommended 7 hours of sleep. The goal of the 11 hours TIB protocol was for participants to reach ≥ 9 hours of sleep. Participants were given at least one night of habitual sleep as a washout. Laboratory testing took place at the same time in the morning for each participant after an overnight fast.

Relevant to Secondary Outcomes

On the fifth day of 8 or 11 hours TIB, participants performed three 10-minute bouts of brisk walking throughout the day. On the night after exercise, participants followed the 8 or 11 hours TIB protocol resulting in six consecutive nights of 8 or 11 hours TIB. The morning after prescribed exercise, participants arrived at the laboratory for cognitive function testing.

Methods

Arterial stiffness

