Peak forearm blood flow was assessed using venous occlusion plethysmography (EC6 system, Hokanson) during reactive hyperemia while participants rested in the supine position. A fitted mercury-in-silastic strain gauge was placed on the left forearm. The forearm was elevated approximately 10cm above heart level with a small occlusive cuff placed around the wrist, and a venous collecting cuff placed around the upper arm that inflated rapidly (E20 inflator, Hokanson). The strain gauge was placed around the widest portion of the forearm. During the forearm blood flow (FBF) measurement, an occlusive wrist cuff was inflated to 200 mmHg while the venous collecting cuff inflated intermittently to 50 mmHg to allow four measurements within one minute. Peak FBF was measured during a three minute period that followed 10 minutes of arterial occlusion (~220 mmHg) at the upper arm. The first measurement took place within 5 seconds after arterial occlusion was released.

Cognitive function

Participants completed a computerized battery of tests from Automated Neuropsychological Assessment Metrics software (VistaLife Sciences). The tests and order of presentation were as follows: Manikin test (spatial rotation ability), task switching (mental flexibility), and the Stroop color-word test (executive function). The software kept the same order of tests for each study visit but changed the presentation sequence within each test to reduce variance in performance scores due to the practice effect.

Statistical analysis

A two-tailed paired t-test was used to compare variables between TIB protocols for primary outcome variables (arterial stiffness, cerebral vascular reactivity, nighttime pulse pressure, peak reactive hyperemia). A two-way repeated measures ANOVA (TIB x Pre/Post Exercise) was used to evaluate the main effect of exercise on cognitive function. A Bonferroni post-hoc test was used to assess differences upon a significant main effect. Statistical significance was set a priori at $P<0.05$.

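### The ANOVA's exercise main effect on cognition cannot be credited to exercise, because Pre/Post is not randomised and is aliased with test session

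*Combined protocol and SAP*

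**What the plan says.** The Statistical analysis section gives the cognitive analysis one purpose: "A two-way repeated measures ANOVA (TIB x Pre/Post Exercise) was used to evaluate the main effect of exercise on cognitive function". It adds: "A Bonferroni post-hoc test was used to assess differences upon a significant main effect". It mentions no term for period or session and no follow-up for the interaction.

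The Study Design section randomises only the sleep condition: "This study utilized a randomized, crossover design that consisted of five consecutive nights of 8 or 11 hours time in bed (TIB) each night". The part on secondary outcomes applies the walking to both conditions: "On the fifth day of 8 or 11 hours TIB, participants performed three 10-minute bouts of brisk walking throughout the day". It continues: "On the night after exercise, participants followed the 8 or 11 hours TIB protocol resulting in six consecutive nights of 8 or 11 hours TIB", and then: "The morning after prescribed exercise, participants arrived at the laboratory for cognitive function testing". No period without walking, no exercise control group and no counterbalancing of Pre and Post are described.

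The Cognitive function section recognises practice as an issue. It says the software "changed the presentation sequence within each test to reduce variance in performance scores due to the practice effect".

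**The concern.** A main effect of exercise needs a comparison in which exercise differs and the rest is balanced. Here the only comparison is Post against Pre, and Post is always the later session of its TIB period. A participant who improves through familiarity with the battery, or through a further night of the assigned TIB, shows the same contrast as one who improves because of the walking. Practice could equally hide a harmful effect of exercise.

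The randomised crossover does support two cognitive questions: whether TIB changes performance, and whether TIB changes the Pre-to-Post change. Both are already in the two-way ANOVA, but the plan names neither as a test of interest. It also ties post-hoc testing to a main effect. Each factor has two levels, so the interaction is the term that would need follow-up comparisons, and none is stated for it.

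At stake is the interpretation of the secondary cognitive outcome. The four primary outcomes use separate paired t-tests and are not touched.

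**Working it through.** The plan states no sample size, SD, effect size or power for cognition, so there is no figure to reproduce. The check concerns the design, followed by an illustration on assumed values.

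**1. Can exercise be separated from session?** Take four cognitive sessions per participant (Pre and Post in each of two TIB periods, as the ANOVA implies), six participants and two balanced sequences.

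| Model | Rank | Reading |
|---|---|---|
| Participant + session (4 levels) | 9 | base |
| base + Pre/Post | 9 | Pre/Post adds nothing: aliased |
| base + TIB | 10 | TIB estimable |
| base + TIB + TIB x Pre/Post | 11 of 11 columns | both estimable |

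A column for nights of TIB (6 at Post, 5 assumed at Pre) is likewise not separable from Pre/Post. The day of the Pre test is not stated, but Pre precedes exercise by definition, so the aliasing with session does not depend on it.

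**2. How much practice enters each effect?** Let m1 to m4 be the expected session means with no exercise effect, in units of the first-retest gain g.

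Pre/Post effect = ½(m2 − m1) + ½(m4 − m3)

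- Gain recurs at every session (0, 1, 2, 3): ½(1) + ½(1) = 1.0g
- Gain halves each session (0, 1, 1.5, 1.75): ½(1) + ½(0.25) = 0.625g
- Gain at first retest only (0, 1, 1, 1): ½(1) + ½(0) = 0.5g

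With balanced sequences, each TIB condition occupies each period equally often, so a common practice curve puts 0g into TIB and 0g into TIB x Pre/Post.

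With an assumed 12:8 split and no period terms, the weights differ by 0.6 − 0.4 = 0.2:

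- TIB absorbs 0.2 × (period 2 mean − period 1 mean): 0.2 × (2.5 − 0.5) = 0.4g, 0.2 × (1.625 − 0.5) = 0.225g, and 0.2 × (1 − 0.5) = 0.1g.
- The interaction absorbs 0.2 × [(m4 − m3) − (m2 − m1)]: 0, −0.15g and −0.2g.

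**3. What could this do to the significance test?** Assume no exercise effect, a within-period Post − Pre change with SD 1, and correlation ρ between the two periods' changes. The mean of the two changes has SD √((1+ρ)/2). The test is a two-sided t on N − 1 degrees of freedom with noncentrality √N × a × g / √((1+ρ)/2), where a is 1.0, 0.625 or 0.5. For N = 20, ρ = 0, a = 1.0 and g = 0.5, this is 4.472 × 0.5 / 0.7071 = 3.16, which gives 85%.

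Probability of P<0.05 for exercise when it has no effect, for g = 0.2 / 0.3 / 0.5 SD:

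| Assumed N and ρ | Recurs | Halves | First retest only |
|---|---|---|---|
| N = 20, ρ = 0 | 22% / 44% / 85% | 12% / 20% / 47% | 9% / 15% / 32% |
| N = 20, ρ = 0.5 | 17% / 31% / 69% | 9% / 15% / 34% | 8% / 11% / 23% |
| N = 15–28, ρ = 0–0.5 | 13–30% / 24–58% / 55–95% | – | 7–11% / 10–19% / 18–44% |

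If the session effect is instead expressed in SDs of the averaged difference (equivalent to ρ = 1 with a = 1.0), N = 20 gives 14% at 0.2 SD and 57% at 0.5 SD. At g = 0 the rate is 5% throughout.

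**The case against.** The strongest case has five parts.

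- **Separation under assumptions.** The aliasing is shown against a four-level session factor. If practice is linear and there is no other period effect, a model with linear session and without period has full rank (10 of 10), so Pre/Post can be estimated. Period x Pre/Post is also estimable and gives evidence on whether practice decays. This is true, but the first model rests on assumptions the design cannot verify, and it becomes inestimable once period is added (rank 10 of 11 columns). Neither model separates the additional TIB night from exercise.
- **Intent.** The project title and the title of one cited article present the work as a question about sleep duration, and the ANOVA already yields the TIB terms. Main effect is also the ordinary label for an ANOVA factor. That makes this more a fault in the named target than in the model. The titles do not alter the analysis sentence, which names exercise alone.
- **Handling of practice.** Varying the presentation sequence may reduce memorising of items. It does not separate a mean gain from exercise.
- **Assumed size.** N, g, ρ and the practice pattern are all assumed, and the highest rates pair the most persistent practice with uncorrelated periods. Prior familiarisation with the battery cannot be ruled out from this short document and would make g smaller. This objection stands in full as regards size.
- **Low stakes.** The outcome is secondary and the data are already collected. That limits the consequence but does not remove the fault.

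**Conclusion.** The concern holds. The one effect the plan names for cognition cannot be attributed to exercise, because Pre/Post is not randomised and is aliased with session. This conclusion follows from the design and needs no assumption about sample size or variability. The direction and size of any actual bias are unknown. Practice contributes 0.5g to 1.0g under the three patterns considered, and the false-positive rates are illustrations on assumed values only. If the Pre/Post result was null, no false claim of benefit arises, although an adverse effect could have been masked. The fault is confined to the Pre/Post main effect and the post-hoc tests that depend on it. The randomised TIB effect and the TIB x Pre/Post interaction are sound under balanced sequences.

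**What to change.** - Name the TIB main effect and the TIB x Pre/Post interaction as the effects of interest for cognition.
- Include period in the model; TIB, Pre/Post, their interaction and period together have full rank (10 of 10). Period x Pre/Post can be added with both targets still estimable (11 of 11). It protects the interaction if the sequences are unequal in size, and it shows whether the session change differs between periods.
- Report the Pre/Post main effect as change between sessions (exercise, practice and any additional night combined), with no causal claim about exercise.
- State how a significant interaction is followed up, since the Bonferroni rule covers main effects only.

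The cost is revised SAP wording and re-analysis of data already collected; no new data are needed. What is lost is an exercise claim that the design cannot support.

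### The cognitive ANOVA has no period or session-order term, so a practice gain that differs between periods weakens and miscalibrates the TIB x Pre/Post test, and biases it if the two orders are unequal in size

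*Combined protocol and SAP*

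**What the plan says.** The Study Design section (Relevant to Primary Outcomes) sets out the crossover: "This study utilized a randomized, crossover design that consisted of five consecutive nights of 8 or 11 hours time in bed (TIB) each night". On allocation it says only: "Participants were randomly assigned based on a random allocation sequence generated in Microsoft Excel". No blocking and no number per order are stated. Between conditions, "Participants were given at least one night of habitual sleep as a washout".

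Under Relevant to Secondary Outcomes, "The morning after prescribed exercise, participants arrived at the laboratory for cognitive function testing". That is the only cognitive visit the design text describes. The earlier visit in each condition is inferred from the Pre/Post label in the analysis: "A two-way repeated measures ANOVA (TIB x Pre/Post Exercise) was used to evaluate the main effect of exercise on cognitive function".

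The Cognitive function section recognises practice. Its one stated countermeasure is that the software "changed the presentation sequence within each test to reduce variance in performance scores due to the practice effect". No familiarisation session is described.

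The follow-up rule is: "A Bonferroni post-hoc test was used to assess differences upon a significant main effect". No rule is given for the interaction.

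**The concern.** Taking the Pre session as inferred, each participant sits the same battery four times in a fixed chronology: Pre and Post in the first period, then Pre and Post in the second. Reshuffling items may limit memory for particular items. It does not stop people getting better at the tasks, and a night or more of habitual sleep does not erase learning.

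Learning curves often flatten. If this one does, the gain from session 1 to 2 exceeds the gain from session 3 to 4. Which TIB condition receives the larger gain then depends on the participant's order, and the two-factor ANOVA cannot see order.

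The TIB x Pre/Post interaction is the only randomised test in this model of whether sleep duration changes the cognitive response after exercise. If its error term carries unmodelled practice, a null result becomes more likely for a reason unrelated to sleep. A period main effect cancels out of this contrast, so adding a period term alone would not help; period x Pre/Post is the term needed.

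**Working it through.** The documents give no N, SD, power, order counts or practice size, so there is no stated figure to reproduce. What follows is algebra plus simulation under stated assumptions.

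**Inputs from the documents:** two conditions in two possible orders; factors TIB and Pre/Post only; two-sided alpha 0.05.

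**Assumed:** N = 20; c = 0.25, 0.5 or 1; true interaction theta = 0.66 where power is shown. All are in units of the within-order SD of the contrast D defined below.

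**Step 1, the contrast.** For each participant let D = (Post - Pre at 11 h) - (Post - Pre at 8 h). The ANOVA interaction F is the square of the one-sample t on D.

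**Step 2, its expectation.** Let g1 and g2 be the practice gains in periods 1 and 2, and c = g1 - g2.
- 8 h first: E[D] = theta + g2 - g1 = theta - c.
- 11 h first: E[D] = theta + g1 - g2 = theta + c.

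**Step 3, bias.** With nA participants taking 8 h first and nB taking 11 h first, bias = -c(nA - nB)/N.
- 10/10: 0.
- 12/8: 4/20 = 0.2, so 0.10 SD (c = 0.5) or 0.20 SD (c = 1) in size.
- 13/7: 6/20 = 0.3, so 0.15 or 0.30 SD.
- 14/6: 8/20 = 0.4, so 0.20 or 0.40 SD.

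The sign reverses if the imbalance goes the other way.

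**Step 4, error variance.** With fraction f in one order, the variance the ANOVA uses is multiplied by about 1 + 4f(1 - f)c². At f = 0.5 this is 1 + c²: 1.06, 1.25 and 2.00 for c = 0.25, 0.5 and 1. With equal orders the mean of D is no more variable than before. The standard error is simply too large, so the test is conservative and loses power.

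**Step 5, simulation (at least 100,000 trials per setting).** The adjusted test averages D within each order, takes the unweighted mean of the two averages, and uses the pooled within-order SD on N - 2 df.

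| Orders | c (SD) | Planned type I error | Planned power, effect opposed by bias | Planned power, effect in direction of bias | Adjusted power |
|---|---|---|---|---|---|
| 10/10 | 0.25 | about 4% | 78% | same | 80% |
| 10/10 | 0.5 | 2.9% | 72% | same | 80% |
| 10/10 | 1 | 0.6% | 49% | same | 80% |
| 12/8 | 0.5 | 4.4% | 57% | 85% | 78% |
| 12/8 | 1 | 3.0% | 21% | 80% | 78% |
| 13/7 | 0.5 | 6.5% | 50% | not tabulated | 76% |
| 13/7 | 1 | 7.5% | 12% | not tabulated | 76% |
| 14/6 | 0.5 | about 10% | not tabulated | not tabulated | 73% |
| 14/6 | 1 | about 16.5% | not tabulated | not tabulated | 73% |

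The adjusted test held type I error at about 5% throughout.

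**Step 6, how likely is imbalance?** If the Excel sequence was unrestricted, nA is binomial(20, 0.5). A split of 12/8 or worse has probability 0.50, and 14/6 or worse has probability 2 x P(nA ≥ 14) = 0.12. Averaged over such allocation, the planned test has type I error of about 5% and power of about 78%, 71% and 50% for c = 0.25, 0.5 and 1.

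**The case against.** The strongest objection is relevance. The plan names the exercise main effect as the ANOVA's purpose, states no interaction hypothesis, and treats cognition as secondary. For that main effect, Post follows Pre in both periods, so the mean practice gain (g1 + g2)/2 enters in full whatever the order balance. At N = 20, a mean gain of 0.25, 0.5 or 1 SD of a participant's average Post - Pre change would produce a false exercise effect in 19%, 57% and 99% of trials. Order terms do not cure this. The objection stands as a limit on what the fix achieves. It does not remove the point, because the interaction is part of the specified two-way model and is its randomised comparison.

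A reader might infer that the planned ANOVA generally inflates false positives. The figures do not support that. At 10/10 and 12/8 the type I error is below 5%, inflation starts at about 13/7, and over unrestricted allocation the rate is about 5%. The documents neither report nor exclude an imbalance.

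A reader might also take 21% as the typical power at c = 1 SD. It is the adverse direction at 12/8; the other direction gives 80%.

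Finally, only the difference between the two gains matters, not practice itself. The document gives no evidence on the shape of the learning curve. With c = 0.25 and equal orders the loss is about 2 points.

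**Conclusion.** The point holds as a weakness of the cognitive analysis. The mechanism follows from the stated design and model: a gain that differs between periods moves the interaction contrast by -c in one order and +c in the other, and nothing in the ANOVA absorbs it. The general consequence is lost power and a test that does not run at its nominal level. At N = 20 and 10/10 the loss runs from about 2 points (80% to 78%) at c = 0.25 SD to about 31 points (80% to 49%) at c = 1 SD. Bias is conditional on unequal realised orders, and type I inflation on a split of about 13/7 or worse.

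The size rests entirely on assumed N, SD, c and order counts, and the four-session timeline rests on an inferred Pre session. The documents do not show that the reported cognitive result is wrong. They show that a null interaction from this model could not be separated from an error term inflated by practice. For a secondary outcome with a cheap remedy, this should be changed but is not critical.

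**What to change.** Analyse each cognitive score with a linear mixed model: fixed effects for TIB, Pre/Post, TIB x Pre/Post, period and period x Pre/Post, and random effects for participant and participant-by-period. Read the sleep effects from the TIB and TIB x Pre/Post terms.

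For the interaction, the simple version is to test the unweighted mean of the two order-specific mean contrasts on N - 2 df. With complete data the mixed model gives the same estimate. Its error term matches that test only if a participant-by-Pre/Post random effect is also included.

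Also:
- report the number of participants in each order;
- confirm that a Pre session took place in each condition, and when;
- state the interaction test and its follow-up rule;
- say in the conclusion that the exercise main effect includes any practice gain and that this model does not separate the two.

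The cost is SAP wording and a re-run on data already collected. If c is in fact zero, the order terms cost about 0.2 points of power at 10/10, 2 at 12/8 and 7 at 14/6.
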